Overall, 53 patients (12%) experienced ischemic vascular SAEs: 28 (6%) had cardiovascular SAEs, 18 (4%) had cerebrovascular SAEs, and 16 (4%) had peripheral vascular SAEs. The most commonly reported SAEs were MI/AMI (14/449: 3%), CAD (10/449: 2%), and CVA (9/449: 2%). Four fatalities were reported due to events in this MedDRA preferred-term search: AMI (considered by the investigator to be possibly related to ponatinib), CAD, cerebral ischemia, and hemorrhagic cerebral infarction. Of 22 patients with SAEs of MI/AMI or CAD, 14 developed CHF concurrent or subsequent to the myocardial ischemic event. Ten of the 18 patients with SAEs of cerebrovascular ischemic events developed stenosis of large arterial vessels of the brain (eg, carotid, vertebral, middle cerebral artery). Ponatinib was withdrawn for 7 patients due to AEs in this group of preferred terms: CAD, hemorrhagic cerebral infarction, cerebral infarction, cerebral infarction with cerebral artery stenosis, CAD and myocardial ischemia with peripheral arterial occlusive disease (PAOD), CVA, and peripheral ischemia. The hemorrhagic cerebral infarction (considered by the investigator not related) was fatal, and peripheral ischemia and CAD/PAOD (considered by the investigator possibly/probably related) were reported as not resolved. All other events were reported as resolved. Most other patients' SAEs in this list of preferred terms also resolved, either with dose adjustments or no change to the dose. Almost all patients with ischemic vascular SAEs had at least 1 risk factor, and most had more than 1.

Peripheral arterial occlusive events, including fatal mesenteric artery occlusion and life-threatening peripheral arterial disease, have occurred in ponatinib-treated patients. Patients have developed digital or distal extremity necrosis and have required amputations. Peripheral vascular SAEs were also reported in the AP24534-07-101 trial. Angina pectoris and MI were reported as treatment-related SAEs. One case of cerebral infarction in the expanded access program was considered by the investigator possibly related to ponatinib.

- **Venous Thromboembolism**

In AP24534-10-201, venous thromboembolic events were observed in 5% (23/449) of ponatinib-treated patients, including deep venous thrombosis/venous embolism/venous thrombosis (11 patients), pulmonary embolism (6 patients), superficial thrombophlebitis (3 patients), retinal vein thrombosis (2 patients) and 1 case each of portal vein thrombosis, and veno-occlusive liver disease. Consider dose interruption of ponatinib in patients who develop serious venous thromboembolism.

Neuropathy

Similar to vascular occlusion, a prospectively defined, MedDRA-based search strategy, containing nearly 300 preferred terms, was employed in the summarization of neuropathy events. Events were further classified as peripheral or cranial neuropathy.

Peripheral and cranial neuropathy has occurred in ponatinib-treated patients. Monitor patients for symptoms of neuropathy, such as hypoesthesia, hyperesthesia, paresthesia, discomfort, a burning sensation, neuropathic pain or weakness. Consider interrupting ponatinib and evaluate if

suspected.

In AP24534-10-201, neuropathy events were observed in 14% (65/449) of patients (cranial in 1% (6/449) and peripheral in 13% (59/449). The most common events were peripheral neuropathy (4%), paresthesia (4%), hypoesthesia (2%), and hyperesthesia (1%). Of the patients who developed neuropathy, 31% (20/65) developed neuropathy during the first month of treatment. One patient discontinued therapy because of neuropathy events (IVth nerve paralysis).

Hepatotoxicity

Liver function test abnormalities are seen with ponatinib, and hepatic failure has been reported. Hepatotoxicity, most commonly manifested by reversible transaminase and alkaline phosphatase elevation and hyperbilirubinemia, has been observed in patients taking ponatinib. Fulminant hepatic failure leading to death occurred in a patient within one week of starting ponatinib. Two additional fatal cases of acute liver failure also occurred. The fatal cases occurred in patients with blast phase CML or Ph+ ALL. Severe hepatotoxicity occurred in all disease cohorts.

Monitor liver function tests at baseline, then at least monthly or as clinically indicated. Interrupt, reduce or discontinue ponatinib as clinically indicated.

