All other TEAEs occurred in fewer than 10% of patients, and no events of pancreatitis were reported. There were no grade 4 events. One grade 5 event was reported (preferred term: pneumonia, reported as related to ponatinib treatment). Grade 3 TEAEs in more than 1 patient included: abdominal pain and lipase increased (3 each) and anemia, nausea, vomiting, fatigue, and hypertension (2 each).

Ten patients had at least 1 SAE. Gastrointestinal disorders (5 patients), and Cardiac disorders, General disorders and administration site conditions, and Infections and infestations (2 patients each) contributed the majority of SAEs. By preferred term, the most common SAEs were:

- abdominal pain (4, 11.4%)
- fatigue, nausea, and vomiting (2, 5.7% each)
- intestinal abscess, duodenal stenosis, hypercalcemia, hypoxia, MI, pneumonia, and right ventricular dysfunction (each in single patients, 2.9% each)

Seven patients discontinued the GIST study due to development of AEs. Most patients had been receiving ponatinib for less than 2 weeks at the time of event onset; most events were considered at least possibly related to treatment.

A Comprehensive Adverse Events and Potential Risks (CAEPR) list using NCI Common Terminology Criteria for Adverse Events (CTCAE) terms is included in **Section 7.1** of the protocol.

Vascular Occlusion

Arterial and venous thrombosis and occlusions, including fatal myocardial infarction, stroke, stenosis of large arterial vessels of the brain, severe peripheral vascular disease, and the need for urgent revascularization procedures have occurred

in at least 27% of ponatinib-treated patients from the phase 1 and phase 2 trials. Ponatinib can cause fatal and life-threatening vascular occlusion within 2 weeks of starting treatment.

Ponatinib can also cause recurrent or multi-site vascular occlusion. The median time to onset of the first vascular occlusion event was 5 months. Ponatinib can cause fatal and life threatening vascular occlusion in patients treated at dose levels as low as 15 mg per day. Patients with and without cardiovascular risk factors, including patients age 50 years or younger, experienced these events. Vascular occlusion adverse events were more frequent with increasing age and in patients with prior history of ischemia, hypertension, diabetes, or hyperlipidemia

Vascular Occlusion Incidence in Ponatinib-Treated Patients in Phase 2 Trial According to Risk Categories

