	Prior history of ischemia, hypertension, diabetes, or hyperlipidemia	No history of ischemia, hypertension, diabetes, or hyperlipidemia
Age: 49 or younger	18% (6/33)	12% (13/112)
Age: 50 to 74 years	33% (50/152)	18% (20/114)
Age: 75 and older	56% (14/25)	46% (6/13)
All age groups	33% (70/210)	16% (39/239)
Total		24% (109/449)

• Arterial Thrombosis

Cardiovascular, cerebrovascular, and peripheral vascular thrombosis, including fatal MI and stroke have been observed in ponatinib-treated patients. *Patients with cardiovascular risk factors are at increased risk for arterial thrombosis with ponatinib; therefore, these patients are excluded for this protocol.* Monitor patients for arterial thrombotic events, and consider interrupting or stopping ponatinib if these events are suspected.

In AP24534-10-201 (phase-2 trial of ponatinib in refractory CML and ALL), 91/449 patients (20%) experienced at least 1 treatment-emergent ischemic vascular event: 55 (12%) had cardiovascular events, 27 (6%) had cerebrovascular events and 36 (8%) had peripheral vascular events.

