3.2.6 History of alcohol abuse

3.2.7 Have uncontrolled hypertriglyceridemia (triglycerides >450 mg/dL).

3.2.8 Patients who are receiving any other investigational agents.

3.2.9 Patients with history of clinically significant bleeding disorder.

3.2.10 Pregnant women are excluded from this study because ponatinib can affect embryo-fetal development. Because there is an unknown but potential risk for adverse events in nursing infants secondary to treatment of the mother with ponatinib breastfeeding must be discontinued.

3.2.11 Patients who are incarcerated are not eligible.

3.2.12 Patients with any history of arterial thromboembolic disease. *Any patient with a history of MI, stroke, TIA, unstable angina or peripheral vascular disease will not be eligible.*

3.2.13 Patients with history of recurrent venous thromboembolism (deep venous thrombosis or pulmonary embolism) or history of venous thromboembolism within 6 months prior to registration on study will not be eligible

3.2.14 Patients with history of active hepatitis B or C infection or chronic hepatitis with Child Pugh B or C hepatic dysfunction.

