5.5 Criteria for Removal from Study

Patients will be removed from study when any of the criteria listed in **Section 5.3** applies. The reason for study removal and the date the patient was removed must be documented in the Case Report Form.

Patients must be discontinued from the trial in the event of myocardial infarction, stroke,

development or progression of arterial disease necessitating revascularization, or other vascular occlusive events.

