Vascular occlusive events have been identified as AESIs for ponatinib. These include arterial and venous thrombotic and occlusive adverse events that meet the criteria for SAEs (cross-refer to the section where the serious criteria are described and defined) and those adverse events that do not meet the SAE criteria. AESIs require ongoing monitoring by investigators and rapid identification and communication by the investigator to the study sponsor. All AESIs, whether SAEs or not, must be reported within 2 business days of the study sponsor awareness to Takeda. Takeda has determined that the events listed below (whether considered serious or non-serious by investigators) should be considered AESIs:

- A. Myocardial infarction: Defined by the Third Universal Definition of Myocardial Infarction
- B. Angina (newly diagnosed or worsening of existing angina or unstable angina)
- C. Coronary artery disease (CAD) (newly diagnosed or worsening of existing CAD) or symptoms that may reflect cardiovascular disease
- D. Cerebrovascular ischemic disease including ischemic or hemorrhagic stroke, vascular stenosis, transient ischemic accident (TIA), cerebrovascular occlusive disease documented on diagnostic neuroimaging, or symptoms that may reflect cerebrovascular disease

- E. New onset or worsening of peripheral artery occlusive disease (eg, renal artery, mesenteric artery, femoral artery) or symptoms that may reflect peripheral vascular disease
- F. Retinal vascular thrombosis, both venous and arterial
- G. Venous thromboembolism where significant compromise of organ function or other significant consequences could result (eg, pulmonary embolism, portal vein thrombosis, renal vein thrombosis) or symptoms that may reflect venous thrombosis

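### Section 2.2.1 says patients with cardiovascular risk factors are excluded, but exclusion 3.2.12 names coronary disease only as MI or unstable angina, so stable coronary disease is not clearly excluded

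*Combined protocol and SAP*

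**What the plan says.** Section 2.2.1 (Vascular Occlusion) identifies who is at higher risk: "Vascular occlusion adverse events were more frequent with increasing age and in patients with prior history of ischemia, hypertension, diabetes, or hyperlipidemia". Under Arterial Thrombosis it adds: "Patients with cardiovascular risk factors are at increased risk for arterial thrombosis with ponatinib; therefore, these patients are excluded for this protocol".

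Section 3 is what determines entry. Exclusion 3.2.12 opens with a general clause on any history of arterial thromboembolic disease, which is not defined, and continues: "Any patient with a history of MI, stroke, TIA, unstable angina or peripheral vascular disease will not be eligible".

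The neighbouring criteria are:
- 3.1.10 admits treated hypertension if blood pressure is controlled.
- 3.1.12 requires an LVEF of at least 50%.
- 3.2.7 excludes uncontrolled triglycerides above 450 mg/dL.
- 3.2.16 excludes antiplatelet agents other than low-dose aspirin.
- 3.2.15, 3.2.19, 3.2.20 and 3.2.21 cover QTc, arrhythmia, uncontrolled illness and congestive heart failure.

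Diabetes appears in no criterion.

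**The concern.** The background promises more than the criteria deliver. Ischemia is the first history it lists as raising the risk, yet the only coronary conditions named in 3.2.12 are MI and unstable angina. Naming only the unstable form invites the reading that stable angina is acceptable. The list is also uneven, because peripheral vascular disease excludes on diagnosis alone while coronary disease appears to need an acute presentation.

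What is at stake is who is exposed. Section 2.2.1 reports that fatal or life-threatening occlusion can occur within the first two weeks of treatment and at 15 mg a day. Aspirin, blood pressure checks, discontinuation rules and expedited reporting all apply once the patient is on drug. Only the eligibility criteria prevent exposure.

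**Working it through.** **Step 1. Compare the criteria with one patient.** Take a patient with stable CAD, no MI, controlled blood pressure, normal LVEF and aspirin 81 mg.

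| Criterion | Stops this patient? |
|---|---|
| 3.2.12, named list | No: neither CAD nor stable angina is named |
| 3.2.12, general clause | Unclear: the term is undefined, and stable CAD need not be thromboembolic |
| 3.1.12, LVEF | No: normal |
| 3.2.16, antiplatelets | No: low-dose aspirin is allowed |
| 3.2.15 and 3.2.19, QTc and arrhythmia | No, unless also present |
| 3.2.20, uncontrolled illness | No: the disease is controlled |
| 3.2.21, heart failure | No |

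So exclusion depends on how one undefined phrase is read.

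**Step 2. Reproduce the protocol's risk table (2.2.1, phase 2 leukemia trial).**
- With a history of ischemia, hypertension, diabetes or hyperlipidemia: (6 + 50 + 14)/(33 + 152 + 25) = 70/210 = 33.3%.
- Without: (13 + 20 + 6)/(112 + 114 + 13) = 39/239 = 16.3%.
- Total: 109/449 = 24.3%.

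These match the printed 33%, 16% and 24%. The crude difference is 33.3 − 16.3 = 17.0 points.

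**Step 3. Adjust for age.** Risk rises with age and the two groups differ in age, so the crude difference overstates the effect of history. The Mantel-Haenszel weight in each band is n1 × n0/(n1 + n0), where n1 and n0 are the numbers with and without a history.

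| Age | With history | Without | Difference (points) | Weight |
|---|---|---|---|---|
| 49 or younger | 6/33 | 13/112 | 6.6 | 33 × 112/145 = 25.49 |
| 50 to 74 | 50/152 | 20/114 | 15.4 | 152 × 114/266 = 65.14 |
| 75 and older | 14/25 | 6/13 | 9.8 | 25 × 13/38 = 8.55 |

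Using unrounded differences: (25.49 × 6.575 + 65.14 × 15.351 + 8.55 × 9.846)/99.18 = 12.6 points.

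**Step 4. Scale to this trial.** Section 12.3 allows at most 45 patients (30 in Cohort A, up to 15 in Cohort B). The share with stable CAD is not given; 2% to 10% is assumed.
- Patients affected: 0.02 × 45 = 0.9 to 0.10 × 45 = 4.5.
- Events avoided, age-adjusted: 0.9 × 0.126 = 0.11 to 4.5 × 0.126 = 0.57.
- Events avoided, crude: 0.9 × 0.170 = 0.15 to 4.5 × 0.170 = 0.77.

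This supposes that replacement patients have none of the listed histories. Since controlled hypertension, diabetes and most hyperlipidemia remain eligible, some will have one, and the gain falls below these figures.

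**The case against.** The strongest reply is that the Section 2.2.1 sentence is loose background and Section 3 governs. Read literally, it would also bar controlled hypertension, which 3.1.10 deliberately admits, so it cannot bind for CAD and be discounted for hypertension. The inconsistency could be removed by correcting that sentence alone. Whether to admit stable CAD would then be a judgement about risk in patients who have run out of standard options (3.1.1). Much of this stands: the sentence is too broad and needs correcting whatever is decided. It does not settle 3.2.12, where the general clause is undefined and coronary and peripheral disease are treated differently without a stated reason.

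The size is also open to challenge, and fairly. The table pools arterial and venous events in leukemia, mixes ischemia with milder histories, and comes from a trial with a median exposure of 508 days. Treatment may be shorter in refractory solid tumors.

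A reader might infer more than the documents support:
- **That the safety sections expect such patients to enrol.** The special-interest list in 7.4 includes "Coronary artery disease (CAD) (newly diagnosed or worsening of existing CAD) or symptoms that may reflect cardiovascular disease". But the same list covers worsening peripheral arterial disease, which 3.2.12 plainly excludes, so its wording shows nothing about eligibility. In 5.5, progression of arterial disease can mean disease undiagnosed at entry.
- **That sites will apply 3.2.12 differently.** All patients are registered centrally and external sites' eligibility is verified centrally (4.1, 4.2), so a uniform reading is possible, though the text does not say which.
- **That prior CAD leads to heart failure on drug.** "Of 22 patients with SAEs of MI/AMI or CAD, 14 developed CHF concurrent or subsequent to the myocardial ischemic event" describes what accompanied or followed on-treatment events, not baseline disease.
- **That diabetes or hypertension should also be excluded.** Nothing in Section 3 suggests that this was intended.

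**Conclusion.** The point holds as a gap in an eligibility criterion. Section 2.2.1 states an intention to keep patients at raised arterial risk off the drug, and 3.2.12 does not clearly carry it through for stable angina, CAD without MI, or earlier revascularization.

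The expected effect is small: at most about 0.1 to 0.6 vascular occlusive events avoided at the age-adjusted difference. That range rests on an unsourced 2% to 10% share, on transporting a leukemia-trial difference to solid tumors, and on replacement patients without a listed history. The true risk in stable CAD could lie on either side of the pooled figure. The case for acting is that the event can be fatal, the protocol already takes this approach to peripheral disease, and the change is cheap. It is a worthwhile correction and not a defect in the statistical design.

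**What to change.** Extend the named list in 3.2.12 so that a history of any of the following makes a patient ineligible: *MI; coronary artery disease; angina, stable or unstable; arterial revascularization; stroke; TIA; carotid or intracranial stenosis that is symptomatic or known to be significant; peripheral vascular disease*. The Eligibility Checklist, which is not among the documents, should follow.

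Replace the Section 2.2.1 sentence with one that matches Section 3: *patients with a history of arterial vascular disease as defined in 3.2.12 are excluded; controlled hypertension (3.1.10), diabetes, and hyperlipidemia other than triglycerides above 450 mg/dL are not exclusions.* If the sponsor prefers to admit stable coronary disease, both places should say so expressly.

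The cost is a few otherwise eligible patients and results that do not cover stable coronary disease. The delay cannot be stated in months, because accrual is governed by the 15/15 split between amplification and mutation/fusion patients and the cap of 10 per tumor type (12.2), not by the pooled rate in 12.3. The 10-then-30 design and its thresholds of 1 and 4 responses do not change.

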AEs, 7 because of progressive disease/lack of efficacy, 6 by either patient or investigator withdrawal or for other reasons, and 5 due to fatal events (4 were cardiac events, discussed above; 1 was due to pneumonia, which was considered not related to ponatinib). The majority of patients treated with ponatinib who have experienced cardiac failure AEs have also experienced vaso-occlusive AEs, either with a direct temporal relationship or, less frequently, with timing that makes a relationship less clear. Almost all patients who experienced cardiac failure events in the absence of vascular occlusive events had a strong history of heart failure, ischemic disease, or structural heart disease.

Hypertension

Patients receiving ponatinib have experienced hypertension and blood pressure should be monitored at each visit. In addition, a home blood pressure assessment will be performed twice per week for patients starting ponatinib, using blood pressure cuff supplied by the study sponsor, Takeda. Patients will be instructed to contact their study doctor and/or study coordinator in the event an at-home blood pressure reading reaches $\geq 160/90$. Any hypertensive measurement will be confirmed by the study team in clinic. For patients who develop HTN or worsening HTN during study treatment, antihypertensive medication should be initiated or optimized to achieve target blood pressure before interruption or dose reduction of the study treatment at the discretion of the investigator. If hypertension is persistent despite adequate anti-HTN therapy including titration of anti-HTN medication or introduction of additional anti-HTN medications, or if grade 4 HTN develops, dose interruption, reduction or discontinuation is recommended. A measurement of $\geq 160/100$ requires dose interruption.

Treatment-emergent hypertension occurred in 67% of patients (300/449) treated with ponatinib. In AP24534-10-201, 9 (2%) patients treated with ponatinib experienced treatment-emergent hypertension as a serious adverse reaction and one patient (<1%) experienced treatment emergent hypertensive crisis as a serious adverse reaction, and required clinical intervention for hypertension associated with confusion, headache, chest pain, or shortness of breath.

In patients with baseline systolic BP<140 mm Hg and baseline diastolic BP<90 mm Hg, 78% (220/282) experienced treatment-emergent hypertension; 49% (139/282) developed Stage 1 hypertension (defined as systolic BP ≥ 140 mm Hg or diastolic BP ≥ 90 mm Hg) while 29% developed Stage 2 hypertension (defined as systolic BP ≥ 160 mm Hg or diastolic BP ≥ 100 mm Hg). In 164 patients with Stage 1 hypertension at baseline, 64% (66/164) developed Stage 2 hypertension. No patients discontinued due to AEs of hypertension, although 6 (2.2%) patients had dose reductions or interruptions due to the event. None of the hypertension events were fatal.

Ocular Toxicity

Ocular toxicities have occurred in clinical trials of ponatinib. Serious ocular toxicities leading to blindness or blurred vision have occurred in ponatinib-treated patients. Conduct comprehensive eye exams at baseline and periodically during treatment.

Retinal toxicities including macular edema, retinal vein occlusion, and retinal hemorrhage have occurred in ponatinib-treated patients (3%). In AP24534-10-201, adverse events in the more-general eye disorders SOC included dry eyes (7%), blurred vision (4%), conjunctivitis (3%), eye pain (3%), periorbital edema (2%), blepharitis (2%), and cataract (2%). Other ocular toxicities

were cataracts, glaucoma, iritis, iridocyclitis, and ulcerative keratitis.

Pancreatitis

Pancreatitis (symptomatic abdominal pain associated with pancreatic enzyme elevation) and/or elevations in lipase and amylase are known AEs associated with ponatinib. Most cases of pancreatitis or elevated pancreatic enzymes occur within the first 2 months of treatment with ponatinib. The events are generally uncomplicated and reversible and can be managed with a brief interruption of treatment and standard medical management. Almost all patients are able to continue with ponatinib treatment at the same or a reduced dose once the event has improved to grade 1 or resolved.

Patients with low-grade (1 or 2) elevation in amylase can be continued without dose reduction but should be monitored closely with serial enzyme level determinations.

Check serum lipase every 2 weeks for the first 2 months and then monthly thereafter or as clinically indicated. Consider additional serum lipase monitoring in patients with a history of pancreatitis or alcohol use. In patients with pancreatitis, do not consider restarting ponatinib until patients have complete resolution of symptoms and lipase levels are less than $1.5 \times$ ULN.

In AP24534-10-201, treatment-emergent pancreatitis occurred in 7% (30/449) of patients (25; 5.6% Grade 3). Pancreatitis resulted in treatment interruption or dose reduction in 6% of patients (26/449). One patient discontinued ponatinib permanently due to pancreatitis. Twenty-three of 29 patients with pancreatitis had resolution of the events within 2 weeks with dose interruption or reduction or with no change in dose; 2 patients had resolution within 4 days with the dose unchanged. The incidence of treatment-emergent lipase elevation was 41% (grade 3 or 4: 18%). Pancreatitis was the DLT from AP24534-07-101 and has been reported in the expanded access program.

Hemorrhage

Hemorrhagic events have been reported with ponatinib (mostly in leukemic patients with grade 4 thrombocytopenia).

Treatment-emergent hemorrhagic events occurred in 25.6% (115/449) of patients, the majority (87, 19.4%) of which were grade 1/2. The most common hemorrhagic events were epistaxis (7.1%), petechiae (3.1%), and ecchymosis (2.2%).

In AP24534-10-201, serious bleeding events were observed in 5.8% (26/449) of patients treated with ponatinib, including 5 fatalities (1 event each of subdural hematoma, traumatic intracranial hemorrhage, hemorrhagic gastritis, intracranial hemorrhage, and hemorrhagic cerebral infarction. One fatality (hemorrhagic gastritis) was assessed by the investigator as possibly related to ponatinib. The incidence of serious bleeding events was higher in patients with accelerated phase-CML, blast phase-CML, and Ph⁺ALL. The most commonly reported serious bleeding events included: gastrointestinal hemorrhage, subdural hematoma (3 patients each, 0.7%); cerebral hemorrhage, hemorrhoidal hemorrhage, retroperitoneal hematoma, epistaxis, post-procedural hemorrhage, traumatic intracranial hemorrhage, gastric hemorrhage (2 patients each, 0.4%). Three patients had their doses reduced or interrupted due to single events each of ear hemorrhage, gingival bleeding, and subarachnoid hemorrhage. Two patients had study drug

discontinued following single events each of cerebral hemorrhage and intracranial hemorrhage. Interrupt ponatinib for serious or severe hemorrhage and evaluate

Fluid Retention

Ponatinib is associated with edema and occasionally serious fluid retention. Patients should be weighed and monitored regularly for signs and symptoms of fluid retention. An unexpected rapid weight gain should be carefully investigated and appropriate treatment provided. Interrupt, reduce the dose of, or discontinue ponatinib according to the recommendations for non-hematologic toxicity.

One or more fluid retention AEs occurred in 125 (27.8%) patients in this study. The most common events were peripheral edema (16.7%), pleural effusion (7.6%), and pericardial effusion (3.8%). In AP24534-10-201, serious fluid retention events were observed in 4% (18/449) of patients treated with ponatinib. One instance of brain edema in a blast phase-CML patient with post-craniotomy was fatal. Serious fluid retention events in more than 1 patient included: pleural effusion (6/449), pericardial effusion (6/449, 1%), and ascites (2/449, <1%). In most cases, patients were able to continue ponatinib therapy without dose reductions or interruptions. Ponatinib was discontinued for three patients, due to pericardial effusion in two, and pleural effusion in one.

Cardiac Arrhythmias

